1.1.3 Clinical Adverse Event Profile

The safety profile of SUBLOCADE injection observed in the Phase 3 studies (RB-US-13-0001, RB-US-13-0003 and INDV-6000-301) was generally consistent with the known safety profile of buprenorphine administered by the sublingual (SL) or buccal routes for the treatment of OUD with the expected exception of injection site tolerability and reactions.

The most common ADRs (reported by $\geq 5\%$ of subjects) with SUBLOCADE were constipation, nausea, hepatic enzyme increased, headache, injection site pain, injection site pruritus, vomiting and fatigue. Injection site reactions were generally mild to moderate in severity, and none were serious. There were no unexpected safety findings. There was no increased risk of suicidality, and opioid OD was reported in $<1\%$ of subjects. There were no cases of SUBLOCADE injection OD reported. There was 1 death reported in the clinical development program, an SAE of gunshot wound with an outcome of death considered not related to study treatment and homicide by the police. There were no reports of subjects who attempted to remove the depot and no reports of buprenorphine OD or respiratory depression. No clinically significant trends in vital signs, electrocardiograms (ECGs), clinical laboratory tests or physical examinations have been noted in any of these studies.

The safety profile of SUBOXONE sublingual film is well characterized and, with the exception of the injection site reactions described above, is similar to that of SUBLOCADE.

1.2 Benefit-Risk Summary

Patients with OUD who survive an OD are at high risk of a subsequent OD. Treatment of OUD patients at high risk of OD (such as when released from incarceration), with methadone or buprenorphine reduces the risk of OD index cases by up to 85% (Marsden 2017). This supports treatment initiation as soon as possible after OD. The literature also supports a clear benefit of higher-dose MAT medications in patients at risk for opioid OD (Dupouy 2017, Marsden 2017, Sordo 2017). As noted above, SUBLOCADE at 300 mg administered subcutaneously on a monthly dosing regimen produces exposures at or above 2 ng/ml consistently, reaching higher exposures that appeared to be associated with improved outcomes. A potential advantage of using SUBLOCADE compared to transmucosal buprenorphine products in the emergency department (ED) following treatment for an opioid OD is the rapid achievement of plasma concentrations of 2 ng/ml buprenorphine which are sustained over the dosing interval. The risks associated with SUBLOCADE administered to patients with OUD in the ED are minimal, largely related to injection site reactions, precipitated withdrawal, or sedation which are significantly less than risk of repeat OD in this patient population.

Because there is a risk of sedation in patients who are not tolerant to opioid effects, patients who have a COWS of <8 and who were released from a controlled environment within the past 30 days will be observed for 2 hours after SUBLOCADE 300 mg administration and discharged with a RASS score > 0. This modification is intended to allow for enrolment of populations (i.e. patients who were recently incarcerated) that are especially vulnerable to opioid overdose due to a loss of opioid tolerance. Studies have shown that opioid overdoses are the leading cause of death in former prisoners in the immediate post-release period (Binswanger et al 2013).

2 STUDY OBJECTIVES

2.1 Primary

The primary objective of this study is:

- Determine the effect of SUBLOCADE treatment after opioid OD when administered in the ED setting, inpatient unit or within 7 days (168 h) of overdose in clinic on repeat OD and death compared to a historical control group and concurrent controls who decline treatment participation.

2.2 Secondary

The key secondary objective of this study is:

- Determine effect of SUBLOCADE when administered in the ED setting, inpatient unit or within 7 days (168 h) of overdose in clinic on treatment engagement at 3 months and 6 months comparing patients who have primarily intravenous to non-intravenous opioid use.

2.3 Exploratory

The exploratory objectives of this study are:

- To determine the effect of SUBLOCADE administered in the ED, inpatient unit or in the clinic within 7 days (168 h) of an opioid OD followed by SUBLOCADE administration monthly on the amount of opioid craving.
- To determine the efficacy of SUBLOCADE administered in the ED, inpatient unit or in the clinic within 7 days (168 h) of an opioid OD followed by SUBLOCADE in the clinic on opioid use as determined by Urine Drug Screen (UDS).
- To evaluate the effect of SUBLOCADE administered in the ED, inpatient unit or in the clinic within 7 days (168 h) of an opioid OD followed by SUBLOCADE in the clinic in the clinic on decision making using a delay discounting task and a brief opioid demand measure to measure craving valuation (hypothetical maximum price participants would be willing to pay for access to opioid, assessing craving/valuation).
- To evaluate the association between participant genetic polymorphisms and subjects with history of OD in subjects that consent to the PGx sub-study.
- To evaluate the relationship between genetics/behavioural laboratory measures of decision making and treatment outcome, including repeat OD in subjects that consent to the PGx sub-study.
- To determine the relationship between decision making and treatment retention and illicit opioid use.
- To evaluate healthcare resource utilisation associated with either treatment regimen as compared to the controls (2015-to end of data collection period) obtained from VCU anonymized health records.
- To assess the impact SUBLOCADE administered in the ED, inpatient unit or in the clinic within 7 days (168 h) of an opioid OD followed by administration of SUBLOCADE in

the clinic on treatment effectiveness as measured by Treatment Effectiveness Assessment (TEA), on medication satisfaction as measured by the Medication Satisfaction Questionnaire (MSQ), and on employment, presentism and absenteeism as assessed by the Work Productivity and Activity Impairment Questionnaire: Specific Health Problem (WPAI:SHP).

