3.3 Exploratory

The exploratory endpoints of this study are:

- Opioid craving in subjects as measured by Craving Visual Analog Scale (VAS) scores.
- Illicit opioid use as measured by urine drug screen (UDS) results.
- Genetic predictors of treatment response and OD.
- Predictability of treatment response based on impulse control as measured by decision making in the delay discounting task, and opioid cravings/valuation as measured by the brief opioid demand task.
- Numbers of ED and hospital visits compared to the historical control (2015-2018) obtained from VCU anonymized health records.
- Scores on Treatment Effectiveness Assessment (TEA), medication satisfaction as measured by the Medication Satisfaction Questionnaire (MSQ), and employment, presentism and absenteeism as assessed by the Work Productivity and Activity Impairment Questionnaire: Specific Health Problem (WPAI:SHP).

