5 STUDY POPULATION SELECTION

5.1 Number of Subjects

Approximately 100 subjects will be enrolled.

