14.2 Sample Size

The study will be powered based upon the primary endpoint, repeat opioid OD and death compared to historical and concurrent control data.

Rationale for sample size: Power calculations: sample size was calculated based on a primary outcome measure of reduced repeat opioid OD rates. Previous research has shown self-reported repeat lifetime OD rates of 15-23% for patients who were seen for an opioid OD (Morizio, Baum et al. 2017).

Based on VCU health system data, for patients seen in the ED for an opioid OD in 2016, 11.5% of those patients were either seen again in the ED for an opioid OD or had died based on Virginia Department of Health death registry data within 6 months after their initial ED visit. Based on power calculations below, with a 3% repeat OD or death rate for the novel treatment group vs. the 11.5% treatment as usual rate in the historical control group, with 99 participants in the novel treatment group and 198 participants in the historical control group there will be a power of 80% at a type I error rate of 5%. See table below. If there is a less than 3% repeat OD rate in the intervention group there will be greater than 80% power.

Fixed Power of 0.80 and sample size for equivalent or non-equivalent numbers of participants per group (intervention vs. historical treatment as usual)

repeated OD/death rate	Stat method	n1:n2 (1:1, 2:1 or :1 ratio)		
11.5% vs 2%	Z-test	86:86	117:59	148:49
	Nonparametric	94:94	148:74	198:66
11.5% vs 3%	Z-test	115:115	160:80	204:68
	Nonparametric	131:131	198:99	265:88

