14.7.2 Secondary/Exploratory Endpoint Analysis

Treatment retention at 3 and 6 months will be analysed utilizing a logistic regression, comparing subjects who have primarily intravenous to non-intravenous opioid use as determined using the MINI.

The analysis of the exploratory endpoints (incidence rate of repeat OD, illicit opioid use as measured by UDS and opioid craving, as measured by the OC-VAS) is detailed in Table 2.

These analyses will be performed using the treatment population.

A summary of the primary, secondary, and exploratory endpoint analyses is shown in Table 2.

Table 2 Summary of Efficacy Analysis Strategy

Endpoint	Statistical Method	Analysis Population	Missing Data Approach	Analysis Timepoint
Primary Efficacy Endpoint:				
Repeat OD or Death	Propensity scores within Cox PH Regression	Treatment	No imputation	EOT (6 months)
Secondary Efficacy Endpoints:				
Treatment retention at 3 and 6 months	Logistic Regression	Treatment	No imputation	EOT (6 months)
Exploratory Endpoints:				
Illicit opioid use as measured by urine drug screen (UDS) results	Hierarchical generalized linear modeling (HGLM)	Treatment	Missing UDS during treatment will be imputed as non-negative for opioids. Missing UDS if lost to follow-up will be imputed as missing.	EOT (6 months)
Opioid craving in subjects as measured by Craving Visual Analog Scale (VAS) scores.	Logistic Regression, ANCOVA	Treatment	No imputation	EOT (6 months)
Genetic predictors of treatment response and repeat OD.	Logistic Regression, ANCOVA	Treatment ^a	No imputation	EOT (6 months)
Predictability of treatment response based on impulse control as measured by decision making in the delay discounting task.	Logistic Regression, ANCOVA	Treatment	No imputation	EOT (6 months)
Retention in treatment between ED initiated Suboxone/Sublocade compared to Outpatient initiated Suboxone/Sublocade	Cox PH Regression	Treatment	No imputation	EOT (6 months)

^a This analysis will only include subjects within the treatment population that consented to participate in the PGx sub-study.

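### Table 2's logistic regression of repeat overdose on genotype rests on about 3 expected events and would often give no finite odds ratio

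*Combined protocol and SAP*

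**What the plan says.** Section 2.3 sets an exploratory objective relating genetics and behavioural measures to "treatment outcome, including repeat OD in subjects that consent to the PGx sub-study". Section 3.3 lists the endpoint as "Genetic predictors of treatment response and OD".

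In Section 14.7.2, Table 2 carries the row "Genetic predictors of treatment response and repeat OD". It assigns logistic regression and ANCOVA with no imputation, and a footnote limits the analysis to treated subjects who joined the PGx sub-study. For a yes/no outcome such as repeat OD, the applicable method is logistic regression. Section 14.7.3 adds that the predictors are polymorphisms in candidate pharmacokinetic and pharmacodynamic genes. For this analysis the plan gives no number of variants, expected PGx consent rate, minimum event count, or penalised or exact method.

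The event rate comes from Section 14.2, where the power statement is made "with a 3% repeat OD or death rate for the novel treatment group". The comparison rate there is 11.5% for usual care, and the group sizes are 99 treated subjects and 198 historical controls. Section 5.1 states: "Approximately 100 subjects will be enrolled".

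**The concern.** Ordinary logistic regression needs events in every genotype group. If a group has none, the maximum-likelihood log odds ratio is infinite, or undefined if there are no events at all, and the Wald test stops being informative. The treated arm is small, the sub-study is optional, and the assumed event rate is low. Controls cannot add events: they come from an anonymised record extract (Sections 6.1 and 13.1.1), while buccal swabs are taken only from consenting subjects (Section 8.8).

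At stake is whether the specified method can return a usable estimate for the repeat-OD part of the genetic objective. The pattern that most favours an association, with every event in carriers, is one the method cannot report sensibly.

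**Working it through.** **Inputs from the documents.** 3% repeat OD or death in the treated group, 11.5% in historical controls, 99 treated and 198 controls, 80% power at 5% type I error (Section 14.2); about 100 enrolled (Section 5.1).

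**Assumed, because the documents do not state them.** PGx consent of 100%, 75% or 50%; a binary carrier genotype with frequency 10% to 50%.

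**1. The plan's own figure.** Exact power of Fisher's test for 3% of 99 against 11.5% of 198 is 80.25% one-sided at 5% (73.0% two-sided). The stated 80% therefore reproduces with these inputs if the test is one-sided; the documents do not state sidedness. This confirms 3% as the planning rate.

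**2. Expected events.** n × 0.03, with P(no events) = 0.97^n:

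| PGx consenters | Expected events | P(no events) |
|---|---|---|
| 100 | 3.0 | 4.8% |
| 75 | 2.25 | 10.2% |
| 50 | 1.5 | 21.8% |

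At n=100 the central 95% range is 0 to 7, and more than 3 events occur with probability 35%. The 3% includes deaths, so repeat OD alone would be no more frequent.

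**3. Chance of a non-finite log odds ratio.** With c carriers among n subjects, event probability p and no true effect, the chance that at least one genotype group has no events is

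(1−p)^c + (1−p)^(n−c) − (1−p)^n.

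For n=100, p=0.03:
- c=10: 0.7374 + 0.0645 − 0.0476 = 0.754
- c=50: 0.2181 + 0.2181 − 0.0476 = 0.389

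| n | p | 10% carriers | 20% | 30% | 50% |
|---|---|---|---|---|---|
| 100 | 3% | 75% | 58% | 47% | 39% |
| 75 | 3% | 81% | 69% | 60% | 54% |
| 50 | 3% | 89% | 82% | 76% | 72% |
| 100 | 11.5% | 29.5% | 8.7% | 2.6% | 0.4% |

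A true odds ratio of 3 or 5 does not remove the problem: at n=100 and 3% overall, the chance is 39% to 63%.

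**4. What the fit looks like.** Take 3 events in 99 subjects, 30 of them carriers. All events fall in one group with probability [C(30,3) + C(69,3)] / C(99,3) = (4,060 + 52,394) / 156,849 = 0.360 under no effect. If all 3 are in carriers, a fitted logistic model returns a standard error of about 15,772 and a Wald p-value of 0.999.

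**5. Power.** For a true genotype odds ratio of 5 at n=100 and 3% overall, two-sided Fisher power is 23% (20% carriers), 18% (30%) and 2% (50%), with no multiplicity correction.

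**6. A continuous predictor, for contrast.** In 20,000 simulated studies with one continuous score at 3%, separation occurred in 0.3% to 0.9% at n=100 and about 3% at n=50, apart from studies with no events.

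**The case against.** The strongest reply is that 3% is a planning value for the primary comparison, not a forecast for this sub-study. Treated subjects are also followed by self-report (Sections 3.6 and 14.7.1) and by monthly calls after stopping treatment (Section 6.4.1), which may capture more events than the emergency department and registry counts behind the 11.5%. The Synopsis gives a still higher background figure: 27% with a second event, 70% of those within 6 months, or 0.27 × 0.70 = 18.9%. A higher treated rate would shrink the problem, as the 11.5% row of the table shows. This stands as a sensitivity, but 11.5% is the plan's usual-care rate. The analysis becomes mostly stable only near the rate at which treatment has no effect.

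It is also fair that the sub-study is optional and exploratory, and that no primary, key secondary or safety conclusion depends on it. That excuses low power, but not the choice of a method that often returns no estimate when an alternative costs almost nothing. Multiplicity control across variants, by contrast, is a preference in a hypothesis-generating analysis.

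A reader might infer four stronger things that the documents do not support:

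- That 3 events is a ceiling. It is an expected count, and more occur about a third of the time.
- That the behavioural predictors fail in the same way. Section 14.7.3 gives abstinence and retention as their outcomes, does not name repeat OD, and uses the whole treatment population. A continuous score rarely separates.
- That the objective as a whole cannot be answered. It covers treatment outcome generally, and retention and abstinence are not limited by the 3% rate.
- That the method itself manufactures false genetic predictors. With 10 carriers in 99, a 2:1 split of 3 events does give Wald p=0.016, but that split has null probability 4,005/156,849 = 2.55% given 3 events. The overall per-variant Wald type I error at n=99 is 2.3%, 1.1%, 0.4% and about 0.01% for 10%, 20%, 30% and 50% carriers, all below 5%. Many variants could still give chance hits, but their number is not stated.

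**Conclusion.** The concern holds for one cell of the plan: logistic regression of repeat OD on genotype among treated PGx consenters. At the plan's rate, the specified estimate would be non-finite in 39% to 75% of studies with full consent, and in 54% to 89% with 75 or 50 consenters. Power is very low even for a large effect.

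These figures rest on the 3% assumption, a binary genotype, carrier frequencies of 10% to 50%, and the assumed consent range. They ease to 0.4% to 30% if the treated rate is 11.5% and everyone consents. The consequence is confined to an exploratory component, so this is a worthwhile correction rather than a threat to the trial's main conclusions.

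**What to change.** In the genetic row of Table 2 and in Section 14.7.3, separate repeat OD from the other treatment outcomes. For repeat OD, replace ordinary logistic regression with event counts by genotype and exact confidence intervals, or with Firth-penalised or exact odds ratios, and label the results descriptive. Keep regression-based genetic inference for the more frequent outcomes already collected: retention at 3 and 6 months, and opioid use by urine drug screen. The objective in Section 2.3 and the endpoint in Section 3.3 can stay if it is stated that the repeat-OD part is descriptive.

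The cost is a wording change, with no new data, visits or subjects. The downside is that there would be no formal Wald test of genotype on repeat OD, a test with very little power at the assumed rate.

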3 STUDY ENDPOINTS

3.1 Primary

The primary endpoint of this study is:

- Time to repeat OD or opioid-related death. Repeat OD or opioid-related death will be measured from electronic medical records and state death registries.
- Additional comparisons on repeat OD and death rates will be made to concurrent patients who decline to participate in the SUBLOCADE injection.

3.2 Secondary

The key secondary endpoints of the study are:

- Numbers and percent of patients in buprenorphine treatment at 3 and 6 months after opioid OD comparing patients who have primarily intravenous to non-intravenous opioid use.

3.3 Exploratory

The exploratory endpoints of this study are:

- Opioid craving in subjects as measured by Craving Visual Analog Scale (VAS) scores.
- Illicit opioid use as measured by urine drug screen (UDS) results.
- Genetic predictors of treatment response and OD.
- Predictability of treatment response based on impulse control as measured by decision making in the delay discounting task, and opioid cravings/valuation as measured by the brief opioid demand task.
- Numbers of ED and hospital visits compared to the historical control (2015-2018) obtained from VCU anonymized health records.
- Scores on Treatment Effectiveness Assessment (TEA), medication satisfaction as measured by the Medication Satisfaction Questionnaire (MSQ), and employment, presentism and absenteeism as assessed by the Work Productivity and Activity Impairment Questionnaire: Specific Health Problem (WPAI:SHP).

3.4 Safety Assessments

Safety assessments include the proportion of subjects with AEs of the following types at any time during the treatment period: at least one AE, a drug-related AE, an SAE, a serious and drug-related AE, or an AE leading to treatment discontinuation.

Additional safety assessments include laboratory assessments, brief physical examinations, vital signs and concomitant medications.

3.5 Health Economics and Outcomes Assessments

Health economics and outcomes assessments include the Healthcare Resource Utilization questionnaire (HCRUQ), the Treatment Effectiveness Assessment (TEA), the Medication Satisfaction Questionnaire (MSQ), and the Work Productivity and Activity Impairment Questionnaire: Specific Health Problem (WPAI-SHP).

3.6 Hypothesis and Treatment Comparisons

Participants who receive SUBLOCADE treatment regimen will have lower repeat OD and death rates compared to controls from electronic health record data. Prospective rates of OD will be based on ED data, self-report data, and Virginia death registry data.

4 STUDY PLAN

4.1 Study Design

4.2 Duration of Treatment

The total duration of study participation will be approximately 7 months. Subjects will be treated for 6 months with an End of Treatment (EOT) visit at 7 months.

Safety follow-up telephone calls will occur 30 days after the EOT Visit if the subject is continuing in treatment, with an additional 5 monthly phone calls (6 months total) if the subject is not continuing in MAT.

5 STUDY POPULATION SELECTION

5.1 Number of Subjects

Approximately 100 subjects will be enrolled.

5.2 Inclusion Criteria

Subjects must meet **all** of the following criteria:

1. Signed the informed consent form (ICF) and have the ability to comply with the requirements and restrictions listed therein.
2. Age: ≥ 18 years at time of executing the ICF.
3. Currently meets DSM-5 criteria for moderate to severe OUD.
4. Is clinically stable (respiratory rate [RR] ≥ 12 , pulse oximetry $> 95\%$, Glasgow Coma Scale [GCS] score of 15) and suitable for the trial in investigator's or designee's judgement.
5. Agrees not to take any buprenorphine products other than those administered during the current study throughout participation in the study.
6. Negative urine pregnancy test for females.
7. Vital signs (BP, HR, temperature) considered within normal limits or non-clinically significant elevation, as assessed by treating physician.

5.3 Exclusion Criteria

A subject will not be eligible for inclusion in this study if any of the following criteria apply:

1. Current diagnosis, other than OUD, requiring chronic opioid treatment.
2. Active suicidal ideation in opinion of the Investigator or designee.
3. Female subject that is lactating, pregnant or planning to become pregnant during their participation in the study.
4. Uncontrolled intercurrent illness including, but not limited to, psychiatric illness/social situations that would limit compliance with study requirements or compromise the ability of the subject to provide written informed consent, signs of opioid toxicity more than 2 hours from naloxone administration or subjects with evidence of pulmonary edema.
5. Known allergy or hypersensitivity to SUBOXONE.
6. Any condition that, in the opinion of the Investigator would interfere with interpretation of subject safety or study results.

-
7. Currently receiving MAT for OUD (e.g. methadone, buprenorphine) or received methadone as a treatment for OUD within 30 days prior to consent.
 8. Concurrent treatment with another investigational agent.
 9. Concurrent enrolment in another clinical study, or observational study that includes MAT.
 10. Treatment for OUD required by court order.
 11. Current or pending incarceration/ legal action that could affect participation or compliance in the study.
 12. Subjects who are unable, in the opinion of the Investigator, to comply fully with the study requirements.
 13. Less than 48-72 hours since last use of long acting opioids (e.g., methadone), by self-report.
 14. Current intoxication with benzodiazepines or alcohol.
 15. Meet current DSM-5 diagnosis for severe Benzodiazepine or Alcohol Use Disorder, or endorse benzodiazepine or alcohol withdrawal symptoms.
 16. Current illicit opioid users who endorse regular use of long acting opioids (e.g. methadone).
 17. Total bilirubin $\geq 1.5x$ the upper limit of normal (ULN), alanine aminotransferase (ALT) $\geq 3xULN$, aspartate aminotransferase (AST) $\geq 3xULN$, serum creatinine $> 2xULN$, international normalized ratio (INR) $> 1.5xULN$
 18. Patients with a history of Long QT Syndrome or an immediate family member with this condition or those taking Class IA antiarrhythmic medications (e.g., quinidine, procainamide, disopyramide) or Class III antiarrhythmic medications (e.g., sotalol, amiodarone) or other medications that prolong the QT interval.

